Block randomization with a block size of four (4) will be used at each site. Each site will receive sets of well-shuffled envelopes in packets of four. A given packet will be completed before the next packet is opened. Each packet of four will contain two cards specifying that a subject should be in the active treatment arm and two cards specifying the placebo arm. This procedure results in six possible different arrangements, for four patients, of the ordering of treatment and placebo assignments. The unblinded Pivotal Study coordinator will record the patient's designation but will not share the assignment with the patient, Investigator, or Statistician.

4) Pivotal Study Schedule; Subject Enrollment and Activities; Monitoring

The Pivotal Study Period will last one hundred and twelve days, beginning with a Pre-Treatment Baseline Period of one Month (28 days), at the end of which the Investigator will reconfirm the appropriateness of the subject's participation in the Pivotal Study, followed by a Treatment Period of three Months (84 days).

As noted, subjects will be advised that during the Pivotal Study Period they may maintain patterns of usage of approved therapeutic medications that they normally use and that they should not initiate new medications, medicating patterns or other interventions. Accommodations for rescue medications will be made, using pharmaceuticals from an approved list developed by the Investigators.

Potential participants will be required to keep a Daily Headache Diary throughout the Pivotal Study Period and, *inter alia*, to document times of CVS-M treatments. They will enter the Daily Headache Diary information using a computer-based system.

The phases and activities of the Pivotal Study are listed below:

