For active-treatment subjects as a group: During the third Month of the Treatment Period, their average total number of Monthly Migraine Headache Days will be lower than their comparable averages derived from the Pre-Treatment Baseline Period.

• Secondary Efficacy Endpoints for the Pivotal Study

- The number of active-treatment subjects having a reduction of 50% or more in Migraine Headache Days during the third Month of the Treatment Period as compared with the Pre-Treatment Baseline Period will exceed the number of placebo-treatment patients having that response rate.
- For active-treatment subjects as a group: During the third Month of the Treatment Period, their average Total Monthly Headache Pain Scores will be lower than their comparable averages derived from the Pre-Treatment Baseline Period.
- For active-treatment subjects as a group: During the third Month of the Treatment Period, their average number of Treated Headaches will be lower than their comparable averages derived from the Pre-Treatment Baseline Period.
- For active-treatment subjects as a group: On average, in comparison with their Pre-Treatment Baseline Period, they will have at the end of the Treatment Period, improvement in scores associated with the Quality of Life and Cognition Assessment measures.

• Safety Endpoint for the Pivotal Study:

The principal safety endpoint for the Study is to verify the absence of material dizziness, with the associated risk of falls, as a consequence of using the active-treatment Device. The Berg Balance test will be used to assess any changes in balance performance as a result of Device usage. Transient nausea and minor dizziness may be experienced by patients, as is sometimes reported in the diagnostic CVS literature, and patients will be trained to verify balance stability after a treatment and before standing up. Previous pilot studies using the Device did not identify nausea or dizziness as side effects attributable to the Device, based on patient self-reporting.

8) Calculating Total Monthly Headache Pain Scores

For each subject the following Total Monthly Headache Pain calculations will be made:

- a. Using the Daily Headache Diary data from the Pre-Treatment Baseline Period, the cumulative Pain Scores for all of the days on which the subject had a Headache during the Month will be calculated; and
- b. For the third Month of the Treatment Period, the cumulative Pain Scores for all of

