the days on which the subject had a Headache during the Month will be calculated.

At the conclusion of the Pivotal Study, Total Monthly Headache Pain score comparisons will be made for each subject: Pre-Treatment Baseline Period vs. the third Month of the Treatment Period. Additionally, such Total Monthly Headache Pain scores for the active-treatment subjects as a group will be compared with those for the placebo-treatment subjects as a group.

9) Statistical Analysis and Pivotal Study Size

As noted above, an experienced, independent and blinded Statistician will be utilized to analyze and summarize the Daily Headache Diaries for all patients. Also, as noted, a blinded Neuropsychologist will analyze and summarize the Quality of Life and Cognition Assessment data, and a Vestibular System Consultant will perform a blinded analysis and summary of the data from the Vestibular Testing Procedures.

Summary of the analytical methodology to be used for the Primary Endpoints

- No prospective stratification: Based on the inclusion and exclusion criteria, there is no medical reason to stratify the Pivotal Study's episodic migraine population.
- **Statistical method**: The Pearson's chi-square test will be used to evaluate the null hypothesis, which is that "There is no difference between the number of Migraine Headache Days (during the third Month of the Treatment Period as compared with the Month during the Pre-Treatment Baseline Period) when comparing subjects treated with the Treatment Device and subjects treated with Placebo Device."

The corresponding alternative hypothesis is that: "There is a reduction in Migraine Headache Days (during the third Month of the Treatment Period as compared with the Month during the pre-Treatment Baseline Period) when comparing subjects treated with the Treatment Device and subjects treated with Placebo Device."

We seek to power the Study so as to reject the null hypothesis and accept the corresponding alternative hypothesis. The following power calculations are based on probabilities from binomial distributions (2-sided test):

- Assumed efficacy metric (response rate): a reduction of 50% or more in Migraine Headache Days with respect to baseline.
- Assumed range of efficacy measured in the placebo arm: 10-15%
- Assumed range of efficacy measured in the treatment arm: 45-55%

Treatment efficacy	Placebo efficacy	Statistical power	Total minimum
			cohort size
45%	15%	80%	72
50%	15%	80%	54
55%	15%	80%	44
45%	10%	80%	50

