50%	10%	80%	40
55%	10%	80%	32

The ONSTIM (occipital nerve stimulator) study (Saper et al.) recorded a placebo (preset stimulation) efficacy of 6% and a responder rate (reduction of 50% or more in headache frequency) of 39%. Results from the PREMICE study (Cefaly, supraorbital transcutaneous neurostimulation) cited by Lambert listed a placebo efficacy of 12.1% and a responder rate of 37%. Both studies evaluated between 60-70 patients. Therefore, the range of 10-15% for placebo efficacy is felt to be relatively conservative as compared with other recent studies involving neuromodulation devices addressing Migraine Headache. The assumed efficacy rate range for the CVS Device is based on non-statistically significant observations in the two previous Migraine pilot studies. We therefore conclude that a total Study size of 80 patients is likely to be sufficient for the most probable outcomes, as that number exceeds the minimum in the table above for the most likely treatment and placebo efficacy cases. For comparison, Topiramate (Topamax) used as a prophylactic migraine treatment reports responder rates in the 37-54% range and a placebo response in the low 20% range. Therefore CVS-M responder rates in the 45-55% range would be clinically meaningful.

• **Cohort size**: Each of the sites will enroll subjects with an overall goal of 80 patients. Once up to 80 subjects have completed the Pivotal Study successfully, enrollment in the Pivotal Study will be stopped (at least temporarily) and the data will be analyzed and summarized. Using expected levels of efficacy for the Treatment and Placebo Devices, this cohort size will likely be more than adequate to demonstrate statistical significance and reject the null hypothesis. The cohort size is also expected to be adequate to establish the low rate of unanticipated adverse events associated with usage of the Device. The Sponsor may choose to extend the Study, with IRB approval, should it be necessary to increase the patient cohort size.

Summary of analytical methodologies to be used for additional safety assessments and for the Secondary Endpoints:

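### Sections 7 and 9 disagree on the 50% responder endpoint: section 7 compares raw counts, while section 9 treats it as a rate per arm but assigns its test to the primary endpoint

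*Combined protocol and SAP*

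**What the plan says.** **Section 7, Secondary Efficacy Endpoints.** The first secondary endpoint concerns patients whose Migraine Headache Days fall by at least half from baseline to the third Month. It says the number of such patients on active treatment "will exceed the number of placebo-treatment patients having that response rate". The sentence gives no denominator, margin, test or significance level. It is the only efficacy endpoint in section 7 that compares the two arms. The primary endpoint and the other three secondary endpoints are changes from baseline within the active arm.

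**Section 9, primary methods.** Under "Summary of the analytical methodology to be used for the Primary Endpoints", the plan says "The Pearson's chi-square test will be used to evaluate the null hypothesis". That null hypothesis compares Treatment Device with Placebo Device, but on the number of Migraine Headache Days. The sample-size text then turns to responders: "Assumed efficacy metric (response rate): a reduction of 50% or more in Migraine Headache Days with respect to baseline". It assumes percentages per arm (10–15% placebo, 45–55% active) and says the "power calculations are based on probabilities from binomial distributions (2-sided test").

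**Section 9, secondary methods.** The list under "Summary of analytical methodologies to be used for additional safety assessments and for the Secondary Endpoints" covers abortive medication and co-morbid symptoms, Quality of Life and Cognition, and Total Monthly Headache Pain. The responder endpoint is not in it.

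**Sections 3 and 9, numbers.** The target is up to 80 patients who complete, half per arm, randomised at each site in packets of four. No dropout rate is given.

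**The concern.** The measure on which the trial is sized appears in three places in three ways: as a count in section 7, as a proportion in the power table, and not at all in the secondary-endpoint methods. An analyst with 7 active and 6 placebo responders could report the endpoint as met under section 7. Another, using the section 9 test, would find the same data far from significant. The plan should settle that choice before the data are seen.

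A count also has a fault that a proportion lacks. If the arms end with different numbers of completers, the larger arm has more chances to produce responders whatever the device does. Because the 80 are completers, equal arms are planned but not assured. Withdrawal can differ between arms, and section 2 lists unwillingness to continue for lack of efficacy among the grounds for withdrawal.

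**Working it through.** **Inputs.** Section 9: placebo response 10–15%, active response 45–55%, two-sided test, 80% in the "Statistical power" column of every row. Sections 3 and 9: 80 completers, planned 1:1, so 40 per arm. Assumed, because not stated: significance level 0.05.

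**Step 1: reproduce the plan's table.** The pooled-variance formula for two proportions, which matches an uncorrected Pearson chi-square, gives per arm

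n = [1.960·√(2p̄(1−p̄)) + 0.842·√(p₁(1−p₁) + p₂(1−p₂))]² / (p₁−p₂)², with p̄ = (p₁+p₂)/2.

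For 45% v 15%, p̄ = 0.30, and n = [1.960·√0.42 + 0.842·√0.375]² / 0.09 = (1.270 + 0.515)² / 0.09 = 35.4. This rounds up to 36 per arm, 72 in total. All six rows computed this way give 72, 54, 44, 50, 40 and 32, exactly the plan's figures. The table is therefore consistent with a two-sided 5% chi-square on responder proportions.

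**Step 2: the count rule, device with no effect.** Let X (active) and Y (placebo) be independent binomial counts with the same response rate p. The literal rule is met when X > Y, with probability Σ P(X = x)·P(Y < x).

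| Completers, active v placebo | p = 10% | p = 15% |
|---|---|---|
| 40 v 40 | 42.5% | 43.7% |
| 42 v 38 | 48.4% | 51.2% |
| 38 v 42 | 36.8% | 36.5% |

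At 40 v 40 ties take 15.0% (p = 10%) or 12.5% (p = 15%), and the remainder splits evenly. For example, (100 − 15.0)/2 = 42.5.

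**Step 3: the section 9 test on the same data.** Summing the same joint probabilities over outcomes where the uncorrected chi-square exceeds 3.84 and active is ahead gives 2.9% at p = 10% and 2.7% at p = 15%, for 40 per arm.

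**Step 4: what each reading requires.** Take 6 placebo responders of 40, and z = (difference in proportions) / √(p̄(1−p̄)·2/40).

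- 7 active: difference 0.025, p̄ = 13/80, z = 0.30. The count rule is met; the test is not significant.
- 13 active: difference 0.175, p̄ = 19/80, z = 1.84. Not significant.
- 14 active: difference 0.200, p̄ = 20/80, z = 2.07. Significant.

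The count rule needs 7 active responders and the test needs 14.

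**Step 5: can packets alone unbalance the arms?** Section 3 says "A given packet will be completed before the next packet is opened", so each site can be out by at most two. Suppose all six listed sites stop half-way through a packet. Each is then two ahead for active with probability 1/6, level with probability 4/6, or two ahead for placebo with probability 1/6. Averaging the count rule over all the resulting arm sizes gives 42.5–43.8%, practically the 40 v 40 result. Packet imbalance is symmetric and does not drive the problem.

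**Step 6: cost in power.** With 40 per arm, the chi-square has 84.7% power at 45% v 15%, rising to 99.6% at 55% v 10%.

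**The case against.** The strongest reply is that sections 7 and 9 should be read together. Section 9 expresses this measure as a rate in each arm, powers it two-sided, names the one test that suits a binary outcome, and aims at statistical significance. Section 7 words every efficacy endpoint as a directional expectation, and nowhere says that one extra responder would count as proof of efficacy. On that reading the chance of a false result in favour of active is about 3%, and the remedy mostly makes explicit what is already intended.

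Much of this stands. A reader might infer from section 7 that the plan has no denominator or test for responders, and so accepts a 43% false-success rate. The documents do not support that: section 9 supplies both a rate and a test, and the 43% applies only if section 7 is read alone. A reader might also infer that part-used packets could produce a gross imbalance such as 46 v 34. Even if all six sites stopped half-way, that needs both opened envelopes to be active at every site, with probability (1/6)⁶ = 1/46,656.

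What the reply does not answer is that section 9 never assigns its test to this endpoint. The heading is for the primary endpoint, the null hypothesis concerns headache days, the secondary list omits responders, and no significance level is given.

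**Conclusion.** The concern holds as an unresolved disagreement between sections 7 and 9 over a secondary endpoint that is also the basis of the sample size. The choice of reading changes the chance that an ineffective device meets the endpoint roughly fifteen-fold: 42.5–43.7% under the literal count, 2.7–2.9% under the section 9 test, both at 40 per arm. A modest excess of active completers (42 v 38) raises the literal figure to 48–51%, and the reverse imbalance lowers it to about 37%.

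These figures rest on independent arms, a common response rate of 10–15% among completers, and an assumed two-sided 5% level. The unequal-arm figures illustrate differential withdrawal and do not predict it. The plan gives no dropout rate, and withdrawal that is itself related to response would change them by an amount the documents give no means to size.

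**What to change.** In section 7, replace the count with a comparison of proportions, for example: *The proportion of patients with a reduction of 50% or more in Migraine Headache Days in the third Month, relative to baseline, will be compared between arms. Each arm will have its own denominator in [named analysis set]. The section 9 Pearson chi-square test will be used at a two-sided 5% level, and the difference in proportions will be reported with its 95% confidence interval.*

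In section 9, list this analysis under the Secondary Endpoints and state the significance level. The sponsor should name the analysis set and say how patients who withdraw are counted.

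The cost is a few sentences, with no new data, visits or patients. The criterion becomes stricter than the literal section 7 wording, but at 40 per arm power stays at about 85% or more across the plan's own assumptions.

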 - o have been diagnosed with migraine with aura
 - have menstrual migraine exclusively

- have been diagnosed with post-traumatic migraine
- o have a history of unstable mood disorder or unstable anxiety disorder
- o use a hearing aid
- have a cochlear implant
- have chronic tinnitus
- have temporomandibular joint disease
- have been diagnosed with traumatic brain injury
- o have been diagnosed with neurological disease other than Headaches
- o have a diagnosed vestibular dysfunction
- o abuse alcohol or other drugs
- are experiencing medication overuse Headaches (individuals with respect to whom the Investigator is concerned that analgesic abuse is involved based on the ICHD-II guidelines).
- o are less than 18 years old or greater than 65 years old
- $\circ~$ have had eye surgery within the previous three months or ear surgery within the previous six months
- have active ear infections or a perforated tympanic membrane
- have participated in another clinical trial within the last 30 days or are currently enrolled in another clinical trial
- are using Botox treatments for migraines.
- Though not excluded, patients taking anti-histamines or anti-nausea drugs will be encouraged not to take such medications within four hours prior to a CVS-M treatment. The Investigator should review other medications taken by the patient with properties that mimic anti-nausea or antidizziness drugs as these may reduce responsiveness of the vestibular system to caloric stimulation. Such medications should also be avoided within four hours prior to a CVS-M treatment.

• Withdrawal Criteria

- Subjects must be withdrawn from the clinical trial if any of the following events occur:
 - A subject does not continue to meet Inclusion/Exclusion criteria.
 - A subject is significantly non-compliant with the requirements of the protocol (Investigator decision).
 - A subject becomes pregnant during the trial as evidenced by a positive pregnancy test.
 - The subject develops an illness (Adverse Event) that would interfere with his/her continued participation.
 - The subject is unwilling to continue due to lack of efficacy.

- The subject withdraws his/her consent.
- The Investigator feels that it is the subject's best interest to be withdrawn.
- Scion Neurostim discontinues the study or has achieved the targeted enrollment.

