- (i) Screening & Baseline Period: Once the subject has been established as having the appropriate Pre-Treatment History, she/he will be asked to complete a review of the informed consent. If the subject agrees to participate in the Pivotal Study, the subject will then complete a Screening Visit. If the subject is recommended for continuation in the Study after the Screening Visit and tentatively approved by an Investigator, she/he will start a Daily Headache Diary and continue to make entries for twenty-eight consecutive days. The Pivotal Study coordinator will complete a Headache History Questionnaire for the subject. The subject will undergo a Vestibular Testing Procedure to establish a baseline record. Any abnormality identified during the Vestibular Testing Procedure for a potential subject will be reported both to the relevant Investigator and to the Vestibular System Coordinator, either of whom can disqualify such potential subject from participating in the Pivotal Study.
- (ii) Clinic Period: After enrollment, the completion of one Month of Daily Headache Diary entries, and reconfirmation by the relevant Investigator of the subject's participation in the Pivotal Study, the subject will come to the clinic for appointments for two days (within the same week) for treatments and for training with respect to use of the CVS-M Device. During the first clinic visit, the subject will complete a Quality of Life and Cognition Assessment exam. Also, women of childbearing age will complete a urine-based pregnancy test to reconfirm that they are not pregnant. The local Pivotal Study coordinator will open, at random, an envelope assigning the patient to the treatment arm or the placebo arm. The second clinic day may be skipped if the Study Coordinator feels that the patient is prepared to use the CVS-M device properly (this should be confirmed with a phone call on the second day). The clinic period is described below.

On each visit during the clinic period, the subject will receive a treatment and be instructed in how to self-administer a defined, controlled treatment using

Version 072414 Schulman Version 4

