CVS has been used extensively and safely in the practice of medicine since its discovery more than a century ago by [name], a discovery for which he received the Nobel Prize in Physiology/Medicine in 1914. There have been no reports in the literature of adverse events or significant negative side effects associated with CVS. The side effect profile from use of the CVS-M Device is expected to be the same as that associated with diagnostic CVS procedures.

CVS-M acts on the central nervous system via the vestibular organs. This mechanism is distinctly different from most forms of neurostimulation that involve either electrical currents applied directly to a target nerve or region (implanted neurostimulators) or a diffuse current to larger areas of the cortex (TMS, CES, tDCS). CVS is non-invasive and easily employed. The SNS CVS-M Device enables its therapeutic use and utility by controlling thermal induction and providing safeguards that ensure treatments remain firmly within parameters established by the supervising physician.

The Berg Balance test (Berg et al.) is well-established and widely used in clinical settings to asses a person's static and dynamic balance abilities. *Inter alia*, the Test is used to quantify clinical improvement or deterioration in patients -- from evaluation of "normals" to assessment of individuals with a wide range of balance impediments. The long form Test consists of 14 balance- related tasks ranging from standing up from a sitting position to standing on one foot. Each task is graded from 0 - 4, and the final measure is the sum from all elements of the Test:

- 41-56 = low risk of fall
- 21-40 = medium risk of fall
- 0-20 = high risk of fall

The Berg Balance test will provide a consistent and easily administered, task-based scheme for identification and quantification of deterioration, if any, of a subject's balance that could be associated with use of the CVS-M Device. The local clinical coordinators will undergo training on administration of the Berg test prior to the Study. Abnormal findings with the Berg test may lead to a more extensive vestibular assessment evaluation. No unexpected side effects, nor any adverse events, have occurred in prior studies utilizing the CVS-M Device.

7) Pivotal Study Endpoints

• Primary Efficacy Endpoint for the Pivotal Study

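### The principal safety endpoint is absence of material dizziness, but it is tied only to a balance-task score that does not record dizziness; the dizziness data collected elsewhere are not linked to it

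*Combined protocol and SAP*

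**What the plan says.** **Endpoint and instrument.** Section 7, Safety Endpoint, opens: "The principal safety endpoint for the Study is to verify the absence of material dizziness, with the associated risk of falls" arising from the active device. It then names the measure: "The Berg Balance test will be used to assess any changes in balance performance as a result of Device usage". The same paragraph accepts that passing nausea and minor dizziness may occur, and has patients trained to check their stability before getting up. It does not define *material*, give a size of Berg change that matters, or state an analysis.

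**What the Berg is.** Section 6: "The long form Test consists of 14 balance- related tasks ranging from standing up from a sitting position to standing on one foot". On scoring: "Each task is graded from 0 - 4, and the final measure is the sum from all elements of the Test". Three fall-risk bands follow, the upper two being "41-56 = low risk of fall" and "21-40 = medium risk of fall".

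**When it is given.** The section 12 table places it at the start of the Pre-Treatment Baseline Period, at the 2-week visit and at the end of the study. The action listed there for on-study results is triggered by a change from the baseline exam.

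**Other dizziness data.** Section 9, under the additional safety assessments, lists dizziness among co-morbid conditions to be assessed from diary entries and Visit Assessments. The blinded Statistician compares the Treatment Period with baseline. The Definitions entry for the Daily Headache Diary, however, names only the day's maximum pain score and the treatment times.

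**The concern.** The endpoint names a symptom, and the measure attached to it is performance on physical tasks. A patient can feel dizzy after treatments at home and still score the same on the Berg at a later clinic visit. If the plan is followed as written, an unchanged Berg score could be reported as showing that material dizziness was absent, although the test does not record dizziness and was not given when dizziness is most expected. The data that do bear on dizziness would sit in a separate summary with no role in the conclusion.

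This matters because it is the trial's principal safety claim for a device that acts on the vestibular system.

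**Working it through.** **Step 1. The plan's own scale.** Section 6 gives 14 tasks, each graded 0 to 4. Maximum = 14 × 4 = 56, which reproduces the top of the low-risk band.

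**Step 2. Content against endpoint.** Section 6 presents the test as task-based and describes no item on dizziness. A change in the score is evidence about balance tasks. No change is evidence only about those same tasks.

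**Step 3. Timing.** Section 4 sets a Treatment Period of 84 days, and section 5 sets two treatments a day: 84 × 2 = 168 scheduled sessions. This is approximate, since the clinic training days describe a single treatment. Of the three Berg tests, one precedes treatment, so 3 − 1 = 2 fall after it starts. Section 5 tells patients that slight dizziness may be felt, particularly towards the end of a session. At the 2-week visit the patient performs a treatment, but section 4(iii) does not say whether the Berg comes before or after it. At the final visit, section 4(iv) has the device returned and specifies no treatment. Neither post-baseline test is therefore assured to follow a session.

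**Step 4. The two data sources side by side.**

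| | Berg (sections 6, 7, 12) | Dizziness entries (section 9) |
|---|---|---|
| Records | Performance on 14 tasks | Dizziness, as a co-morbid condition |
| When | Three visits | Diary and Visit Assessments |
| Named for the principal safety endpoint | Yes | No |
| Comparison with baseline | Yes | Yes |
| Active-versus-placebo comparison stated | No | No |
| Size that counts as material | None | None |

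The source that addresses the symptom is not attached to the endpoint, and the source attached to the endpoint does not address the symptom.

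**Step 5. Sensitivity in this population.** No baseline Berg scores are given. A high baseline is an assumption, drawn from two facts. Section 2 limits age to 18–65 and excludes people who "have a diagnosed vestibular dysfunction", as well as those with other neurological disease or traumatic brain injury. Section 4(i) sends any abnormality on the baseline vestibular test to two people, "either of whom can disqualify such potential subject from participating in the Pivotal Study". If patients' ability exceeds what the tasks demand, mild imbalance may leave every task at full marks. The documents give no sensitivity data, so this remains a possibility without a figure.

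**The case against.** **The Berg may be the intended test of what is material.** Section 7 separates material dizziness, with its fall risk, from the minor and transient kind, and a balance test speaks to fall risk. This stands in part: the Berg is a reasonable check for persistent loss of balance. But the plan does not define *material* in those terms, and dizziness that was substantial after home sessions but had settled by the visit would not be seen.

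**The plan has other safeguards.** Section 9 assesses dizziness, section 4(v) collects adverse events, section 4(iii) refers balance concerns to the Investigator and the Vestibular System Consultant, and section 6 allows fuller vestibular assessment after abnormal Berg findings. All of this stands. A reader might infer that dizziness goes unmeasured, and the documents do not support that. The gap is that these data do not feed the stated endpoint.

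**The fall-risk bands.** A reader might infer that the bands would hide large losses, because a patient could drop one grade on all 14 tasks and remain low risk. This should not be argued. It holds only from a start of 56 (56 − 14 = 42) or 55 (55 − 14 = 41); from 54 the result is 40, medium risk. More importantly, the plan does not use staying in a band as its criterion. Sections 7 and 12 look at any change from baseline, so a 14-point loss would be noticed.

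**The ceiling.** A reader might also infer that a near-maximum start leaves no room to show harm. A high score limits room to improve, not to decline. Only the weaker point in Step 5 survives, and section 6 itself says the test is used in people with normal balance as well as in impaired groups.

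**Conclusion.** The concern holds as a gap in endpoint definition. The principal safety endpoint names dizziness, and its only named instrument is a 14-task balance score with no described dizziness item, taken twice after treatment starts against about 168 scheduled sessions. An unchanged score supports no gross loss of balance-task performance at those visits and nothing stronger.

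This rests on the documents' description of the Berg, its schedule and the section 9 text. It does not depend on the assumed high baseline, which adds only that mild imbalance may go unregistered. How often dizziness would be missed cannot be calculated from the documents. The correction is worth making because it changes what the trial may conclude on safety at little cost.

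**What to change.** Revise the Safety Endpoint paragraph in section 7:

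1. **Dizziness component.** Base it on the section 9 dizziness data: the number of patients with dizziness, and days with dizziness per 28-day Month. Compare active with placebo as well as with baseline. The sponsor should define *material* before the data are analysed.
2. **Confirm the source first.** Check that the diary form records dizziness on all days and not only with headaches, since the diary definition does not mention it. If it does not, use the Visit Assessment entries. These would support counts of patients reporting dizziness at visits, but not days per Month.
3. **Berg reporting.** Report by arm the loss from each patient's own baseline score.
4. **Berg conclusion.** Limit it to balance-task performance at the tested visits.

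**Cost.** Wording and one extra table, with no new test, provided the dizziness entries are collected as section 9 states. The Berg claim becomes more modest. Some recorded dizziness will come from migraine itself. The placebo arm carries the same background, which is why the between-arm comparison is needed beside the comparison with baseline.
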